**A Randomized, Double-Blind, Placebo-Controlled Trial of the Rapid Antisuicidal Effects of
Intranasal Ketamine in Comorbid Depression and Alcohol Abuse**

NCT03539887

Version Date: 10/09/2019

IRB NUMBER: HSC-MS-17-0903
IRB APPROVAL DATE: 10/09/2019

A Randomized, Double-Blind, Placebo-Controlled Trial of the Rapid Antisuicidal Effects of Intranasal Ketamine in Comorbid Depression and Alcohol Abuse

Principal Investigator: [name], PhD, MSc.

Co-Principal Investigators: [name], [name], PhD.

Co-Investigators: [name] [name], [name] [name], MSc., [name], [name] MD, [name] MD, [name] MD, [name] MD.

General Information

Clinicians have a limited ability to predict imminent suicidal behavior and efficacious treatments are not available to treat suicidal patients. Thus, Rapid-acting treatments for suicidal individuals are truly needed. This project aims to evaluate the potential rapid and sustained antisuicidal and antidepressant effects of a single intranasal dose of ketamine in inpatients during a mood episode (in Major Depressive Disorder, MDD or Bipolar Disorder, BD) with or without comorbid recent abuse of alcohol. These results will elucidate the antisuicidal effects of ketamine using the intranasal route along with the identification of associated mediators or moderators; this approach has the potential for enormous public health impact.

Background

Suicide: A Major Public Health Problem

Suicide occurs across demographics and psychiatric disorders, killing at least one million individuals worldwide each year. In contrast to other injury-related death such as homicide or motor vehicle accidents, suicide rates have increased, particularly among middle-aged adults. In the US, each year, hundreds of thousands of Americans seek emergency treatment for suicidal thoughts or behaviors. Unfortunately, even when these individuals are hospitalized on inpatient units or connected with longterm psychiatric resources, they remain at acute risk for suicidal behavior. Over 40,000 Americans killed themselves in 2013 and over 380,000 presented to emergency services for suicidal thoughts and behaviors. In contrast, other forms of preventable death, such as motor vehicle accidents, have declined making suicide the leading cause of injury-related death in the U.S, and arguably, the leading cause of psychiatry-related mortality (Rockett et al 2009).

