Since there is no available studies in this field using the intranasal route and considering that the highest risk times for suicidal behavior are the week after admission to an inpatient psychiatric unit and the week after discharge (Qin & Nordentoft 2005), we aim to investigate the rapid antisuicidal effects of intranasal ketamine in patients with suicidal ideation during depressive episodes with or without recent use of alcohol. We hypothesize that a single dose of intranasal ketamine will induce a rapid, robust and sustained decrease in suicidal ideation in subjects with a comorbid major depressive episode and alcohol dependence relative to only depression and placebo as defined by changes in suicidal ideation scales after 24hrs.

Objectives

Primary objective: To evaluate the rapid antisuicidal effects on a single dose of intranasal ketamine (50mg) in a sample of depression comorbid or not with alcohol abuse compared to placebo.

Secondary objectives:

- To identify clinical variables and dimensions associated with the potential antisuicidal efficacy of intranasal ketamine.
- To identify post-treatment biomarkers associated with the antisuicidal response to ketamine.
- To evaluate the role of recent alcohol abuse in the antisuicidal and antidepressant effects of ketamine
- To identify clinical and biological predictors of response to ketamine
- To evaluate safety and tolerability of intranasal ketamine

Hypothesis:

-Primary: A single dose of ketamine will induce a rapid, robust and sustained decrease in suicidal ideation in subjects with a comorbid major depressive episode and alcohol dependence relative to placebo as defined by change in SSI scale after 24hrs.

-Secondary:

- The antisuicidal efficacy of intranasal ketamine will be independent from its rapid antidepressant efficacy.
- Intranasal ketamine will present superior antisuicidal efficacy in the group with comorbid depression and alcohol compared to depression only.
- Antisuicidal response to ketamine will be correlated with changes in neurotrophic factors and inflammatory markers at one day after ketamine infusion. -Intranasal ketamine (50mg) will be safe and well-tolerated.
- Alcohol use and/or family history of alcohol abuse will be associated with better antisuicidal and antidepressants response to ketamine.

IRB NUMBER: HSC-MS-17-0903

IRB APPROVAL DATE: 10/09/2019

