Our outcome analyses will focus on examining the acute effects and duration of intranasal ketamine treatment during inpatient psychiatric hospitalization. As a primary outcome, we will examine the efficacy of intranasal ketamine for preventing suicidal behavior and ideation among adult patients in a current depressive episode at day 1. Our primary outcome analysis seeks to answer two questions: 1) will intranasal ketamine work acutely compared to placebo, and 2) how long will this effect persist? Effect sizes will be calculated for intranasal ketamine treatment. In the primary outcome analysis, two dichotomous primary outcome measures will be examined in the evaluation: 1) the presence or absence of suicidal ideation, and 2) the presence or absence of suicidal behavior as measured using the C-SSRS and SSI. Our secondary outcome analysis will include an examination of 1) the effects of intranasal ketamine for suicidal ideation while controlling for improvements in depression and other dimensions 2) the potential role of recent alcohol abuse and previous alcohol dependence in the rapid anti-suicidal effects of intranasal ketamine. The symptom severity ratings of SSI, the C-SSRS total score and, as well as changes in MADRS scores will be utilized as primary and secondary outcomes, respectively. Normality assumptions for continuous variables will be examined. Baseline characteristics will be compared between responders and non-responders with the Mann-Whitney U test for continuous variables and the chi-square test for categorical variables. Changes between two time-points for continuous variables were tested with paired t tests, and associations between continuous variables will be quantified with the Spearman correlation coefficient. Random effects models will be performed to quantify changes in clinical score and its component items over time and to compare temporal differences between eventual responders and non-responders.

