Analyses of cross-sectional data with missing values will utilize multiple imputation (Proc MI and Proc MIANALYZE, SAS v. 9.3), while longitudinal analyses will rely on maximum likelihood (in the Bayesian context). Multiple imputation, maximum likelihood, and explicitly modeling missing data in the Bayesian approach are all robust to data missing at random. Sensitivity analyses will permit evaluation of the robustness of findings to missing data assumptions. Pattern-mixture modeling methods will address any identified non-ignorable missing data patterns.

Preliminary data analyses will inspect baseline group differences as well as correlations between baseline covariates and specified criterion variables. Baseline covariates demonstrating a correlation

IRB NUMBER: HSC-MS-17-0903

IRB APPROVAL DATE: 10/09/2019

with both predictors and outcome variables, meet criteria for being potential confounders, and will result in two sets of analyses: one in which the relevant variable is included as a covariate and one in which it is not. This will determine the degree to which any group differences might confound conclusions regarding treatment. Analyses will proceed in parallel using conventional, Frequentist and Bayesian approaches. Frequentist results yield the probability of the observed data, or data more extreme, given that the null hypothesis holds. Bayesian results yield the probability that an alternative holds. Eleven patients per group are required using confidence level of 95% (with $P<0.05$, two-tailed) and power 0.8, based on previous studies using ketamine for depression in placebo-controlled studies reporting response rates of 60% with ketamine and 10% with placebo. The study was designed to detect a moderate to large difference ($d=0.7$) between ketamine vs placebo, based on previous studies using IV ketamine (Wilkinson et al 2018). Treatment effects may be also quantified as mean differences between groups and associated effect sizes are based on standardized mean difference (Cohen's d). All statistical tests were two-sided with an alpha set at 0.05. All analyses were performed using SPSS v. 20 (SPSS Inc., USA) and SAS (version 9.2; SAS, Cary, North Carolina).

References

Andrade C. Intranasal drug delivery in neuropsychiatry: focus on intranasal ketamine for refractory depression. *J Clin Psychiatry*. 2015 May;76(5):e628-31.

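### The only test the plan gives for baseline predictors of ketamine response has no treatment-by-factor term, so general prognostic factors could be reported as ketamine-specific

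*Combined protocol and SAP*

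**What the plan says.** Three places set the question. General Information describes the project as studying ketamine's antisuicidal effect "along with the identification of associated mediators or moderators". The secondary objectives include "To identify clinical and biological predictors of response to ketamine". A secondary hypothesis states "Alcohol use and/or family history of alcohol abuse will be associated with better antisuicidal and antidepressants response to ketamine".

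The Statistics section gives the methods:

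- For baseline factors: "Baseline characteristics will be compared between responders and non-responders with the Mann-Whitney U test for continuous variables", and chi-square for categorical ones. Treatment arm is not mentioned, and the section does not define a responder or say whether responders come from one arm or both.
- For time courses: random effects models that quantify change in scores and also serve "to compare temporal differences between eventual responders and non-responders".
- For alcohol: a secondary analysis of "the potential role of recent alcohol abuse and previous alcohol dependence in the rapid anti-suicidal effects of intranasal ketamine", with no model stated.
- For covariates: those that look like confounders lead to two analyses, "one in which the relevant variable is included as a covariate and one in which it is not". This is a main-effect adjustment.
- For error rate: "All statistical tests were two-sided with an alpha set at 0.05".

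**The concern.** A moderator, or a predictor specific to ketamine, is a baseline factor across which the ketamine-minus-placebo difference varies. Estimating that needs both randomised arms and a treatment-by-factor term. Splitting patients by outcome and comparing their baselines asks who improved. A milder course or a better general prognosis will separate responders from non-responders even if it has nothing to do with ketamine.

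The time-course comparison has a related weakness. Responder status is derived from the scores being modelled, so part of the difference between the groups comes from how they were formed.

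At stake are the secondary conclusions on who benefits from ketamine. These could be carried into later trials as selection criteria.

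**Working it through.** **1. The plan's own sample size.** Inputs from Statistics: 60% versus 10% response, two-sided 0.05, power 0.80. With unpooled variance,

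n = (1.960 + 0.842)² × (0.6×0.4 + 0.1×0.9) / 0.5² = 10.36, rounded up to 11 per group.

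The stated 11 reproduces. It is a calculation for the main effect of treatment and covers no interaction.

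**2. Allocation.** Design describes 1:1 allocation in both alcohol groups, four groups in all. Description of Study Populations gives a total of 60 but lists 30 on ketamine and 15 on placebo, and the text after the list of measures gives about two thirds and one third. I therefore ran 30:30 and 30:15.

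**3. False flags for a purely prognostic factor.** Assumed model: latent improvement L = a(arm) + b·x + e, where x and e are standard normal and b is the same in both arms, so there is no interaction. A patient responds if L > 0. Setting a(arm) = Φ⁻¹(p)·√(1 + b²) with p = 0.6 or 0.1 gives the plan's response rates. The strength b is not in the documents, so a range is shown. Entries are the share of simulated trials with p < 0.05.

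| b (SD per SD of factor) | Mann-Whitney, responders v non-responders | Linear treatment-by-factor test |
|---|---|---|
| 0 | about 5% | about 5% |
| 0.1 | about 7% | about 5% |
| 0.2 | 12–14% | about 5% |
| 0.5 | 46–52% | about 5% |
| 0.8 | 78–81% | about 5% |

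Using ketamine patients alone gives similar rates. One reason is that most pooled responders are ketamine patients: at 30:30 the expected numbers are 30×0.6 = 18 on ketamine and 30×0.1 = 3 on placebo.

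**4. A second model.** Here the factor acts on the log odds of response, with odds ratio 2 or 3 per SD in both arms. The responder comparison flags it in 36% and 67% of trials (30:30 pooled), 34% and 63% (30:15 pooled), and 36% and 66% (ketamine arm only). A linear interaction test on a continuous outcome stays at 4.7% to 5.3%. A logistic likelihood-ratio interaction test runs at 6% to 10%, inflated by the small sample, which favours the continuous SSI outcome.

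**5. Eventual responders over time.** Assumptions: n = 60, baseline SSI mean 20, SD 4, visit noise SD 6, no drug effect, no subgroups, and response defined as at least a 50% SSI fall at 24 h. The 24 h change then differs between the groups so formed in essentially every trial, which follows from the definition. At an earlier visit with independent noise, the rate is about 5% if baseline is error-free and about 25% if baseline carries the same noise. Correlation between visits raises it further; the documents give no correlation. Only about 6–8% of patients are responders in this scenario, so it shows the mechanism and does not forecast this trial.

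**6. Precision of an interaction estimate.** With 15 per cell, the SE of an alcohol-by-treatment interaction in SD units is √(4/15) = 0.516.

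- Power for 0.7 SD: Φ(0.7/0.516 − 1.960) = Φ(−0.60) = 27%. For 1.0 SD it is 49%.
- Interaction detectable with 80% power: 2.802 × 0.516 = 1.45 SD.
- Cell size for 80% power at 0.7 SD: 4 × (2.802/0.7)² = 64.1, so 65.

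**7. Number of factors.** With no multiplicity control, 10 independent null factors tested at 0.05 give 1 − 0.95¹⁰ = 40% chance of at least one false finding, and 20 give 64%.

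**The case against.** The Statistics section never labels the responder comparison as the predictor search, and the stated first use of the random effects model is to describe change over time. On that view the section lists descriptive analyses and the fault would lie only in how they are read. A factor that separates responders within the ketamine arm does forecast who improves after ketamine, and calling it a predictor in that sense is not false. The objection stands in part. The link to the objective is an inference, but no other specified analysis fits it, and both the moderator aim and the alcohol hypothesis ask for more than a forecast.

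Some stronger readings are tempting, and the documents do not support them:

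- A reader might infer that the plan rules out interactions or discards the placebo arm. It does not say so. For alcohol the method is unspecified, and the 1:1 allocation within alcohol groups in Design would support an interaction test.
- A reader might infer that prognostic factors will be misreported. The rate depends on an assumed strength; at 0.1 SD it is barely above nominal.
- A reader might infer that a responder time-course difference is guaranteed throughout. It is built in only at the visit that defines response, and leakage to earlier visits depends on measurement error and correlation.

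The low power of interaction tests is a fair practical objection. It argues for exploratory labelling and intervals, and does not make a test of a different question a substitute.

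**Conclusion.** The concern holds in limited form. Followed as written, the plan's only baseline-predictor test can present a general prognostic factor as specific to ketamine. The size is about 12–14%, 46–52% and 78–81% of trials at assumed prognostic effects of 0.2, 0.5 and 0.8 SD, against about 5% for an interaction test. This rests on the plan's 60% and 10% response rates and on a factor acting equally in both arms. The conclusion is the same under either allocation and whether or not placebo patients are included. The eventual-responder time courses are descriptive and are not evidence of distinct response types. A reader might infer that the main efficacy result is compromised; the ketamine versus placebo comparison does not use these tests and is unaffected.

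**What to change.** Change the Statistics section as follows:

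- Define a responder: scale, threshold and visit.
- Prespecify a short list of baseline factors: recent alcohol abuse, family history of alcoholism, and a few biomarkers from the baseline blood sample.
- For each, fit SSI change at 24 h on treatment, baseline SSI, factor and treatment-by-factor. Report the interaction estimate with its confidence interval as exploratory. This also supplies the missing model for the alcohol analysis.
- Do not use post-treatment biomarkers as interaction terms, because treatment may already have altered them. The objective and hypothesis on biomarker change after dosing need their own association analysis, labelled as such.
- In the random effects model, compare the randomised arms over time.
- Label any retained responder versus non-responder comparison as descriptive or prognostic.

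The cost is wording only, with no new patients or visits. The downside is imprecision: about 27% power for a 0.7 SD alcohol-by-treatment interaction with 15 per cell, so a non-significant interaction would not show that a factor has no modifying role.

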-CNS Studies with Intranasal Ketamine: Intranasal ketamine seems a reasonable choice for further studies in the field. Intranasal ketamine has been successfully used in the treatment of headache and pain in ambulatory patients (Kaube et al 2000, Huge et al 2010, Carr et al 2004). In one study, 50 mg of ketamine administered intranasal was well tolerated and led to symptomatic improvement in chronic pain (Carr et al 2004). In psychiatry, Lapidus et al investigated the potential rapid antidepressant effects of intranasal ketamine (50mg) in subjects with MDD. Patients showed significant improvement in depressive symptoms at 24 hours after ketamine compared to placebo. Response criteria were met by 8 of 18 patients (44%) 24 hours after ketamine administration compared with 1 of 18 (6%) after placebo. Intranasal ketamine was well tolerated with minimal psychotomimetic or dissociative effects and was not associated with clinically significant changes in hemodynamic parameters (Lapidus et al 2014).

IRB NUMBER: HSC-MS-17-0903
IRB APPROVAL DATE: 10/09/2019

Scientific Impact: The opportunity to intervene quickly and decisively to prevent suicidal ideation may improve clinical practice and outcomes for subjects at high risk for suicide. A rapid-acting suicide intervention strategy to prevent suicidal ideation and behavior using a feasible and safe route such as the intranasal for ketamine studies, nested with a comprehensive intervention that addresses underlying suicide risk and protective factors, has the potential for enormous public health impact. There is no study evaluating the rapid antisuicidal effects of intranasal ketamine in patients with suicidal ideation. Also, no study has evaluated the role of alcohol abuse as a moderator of clinical response in depression and suicidality.

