This study will be a double-blind, randomized, placebo controlled trial, evaluating drug-free inpatients (at least 24hs period pre-admission) with depressive episode associated with past suicidal attempt and current active suicidal ideation. Patients will be randomly assigned to intranasal ketamine hydrochloride (50 mg) or saline solution (1 to 1 in both groups, suicide or suicide plus alcohol, with a total of 4 groups). After the single intranasal administration, assessments will occur at +40 min, +240 min, +24 h (phase 1), and +48 h (phase 2). For phase 2, patient may receive their regularly scheduled daily medications if improvement less than 50%. Pts will be subsequently followed up on the suicidal ideation scores until discharge once a day with treatment as usual. This study is expected to take one year to be concluded. Medication should be applied in the first 24hs after admission. There is no approved treatment for suicidal ideation and just a few trials used ketamine for suicidal ideation, none of them evaluating the intranasal route. Thus, a placebo-controlled study is warranted to prevent potential methodological issues. The use of ketamine plus standard care would bias the evaluation of the specific antisuicidal efficacy of intranasal ketamine since standard treatments in some cases may also target suicidality and mood in the short-term.

Assessment of antisuicidal efficacy will be obtained using the Columbia-Suicide Severity Rating Scale (CSSRS) as a screening tool for inclusion (based on "yes" or "no" questions) at HCPC. MADRS item 10 score of 5 or 6 suggests active suicidal risk and will be also used as the threshold for patient inclusion in the ketamine intervention. For those enrolled, the primary efficacy outcome measure will be changes in suicide severity at 24hr post-treatment based on the Scale for Suicide Ideation (SSI) scores, which assesses presence of suicidal ideation and history of suicidal behavior. Secondary outcomes to be administered at each visit include the Montgomery-Åsberg Depression Rating Scale (MADRS), the Young Mania Rating Scale (YMRS), the Clinician-Administered Dissociative States Scale (CADSS), Snaith-Hamilton Pleasure Scale (SHAPS) Alcohol Urge Questionnaire (AUQ) and the Clinician-Administered National Institutes of Health-Brief Fatigue Inventory (NIH-BFI). Inter-rater reliability will be assessed for all ratings, with accepted kappa over 0.8.

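### The moderator and predictor aims have no treatment-by-factor analysis: the named responder comparison tests prognosis, and the alcohol analysis has no stated method

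*Combined protocol and SAP*

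**What the plan says.** **Aims.** General Information includes mediators and moderators among the things to be identified. The Scientific Impact paragraph of the Background claims novelty because "no study has evaluated the role of alcohol abuse as a moderator of clinical response in depression and suicidality". One secondary objective is "To identify clinical and biological predictors of response to ketamine". Two secondary hypotheses are "Intranasal ketamine will present superior antisuicidal efficacy in the group with comorbid depression and alcohol compared to depression only" and "Alcohol use and/or family history of alcohol abuse will be associated with better antisuicidal and antidepressants response to ketamine".

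**Analyses (Statistics).**
- Baseline features against response: "Baseline characteristics will be compared between responders and non-responders with the Mann-Whitney U test for continuous variables and the chi-square test for categorical variables". The section does not define a responder or say whether the arms are pooled.
- Random effects models, used among other things "to compare temporal differences between eventual responders and non-responders".
- Spearman correlations between continuous variables, correlations of baseline covariates with outcomes, and analyses with and without a covariate that looks like a confounder.
- Alcohol: a separate secondary analysis of "the potential role of recent alcohol abuse and previous alcohol dependence in the rapid anti-suicidal effects of intranasal ketamine", with no test or model attached.

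No treatment-by-factor term, and no comparison of the ketamine-placebo difference between alcohol strata, appears anywhere.

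**Layout.** Design randomises "1 to 1 in both groups, suicide or suicide plus alcohol, with a total of 4 groups". Description of Study Populations gives a total of 60 but lists groups of 30 and 15, and splits only the ketamine group by alcohol (15 and 15). The text after the list of measures gives one third on placebo. Inclusion criterion 4 lists current alcohol abuse without limiting it to a subgroup.

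**The concern.** In a placebo-controlled trial, efficacy is a ketamine-placebo difference. Greater efficacy with alcohol comorbidity therefore means that this difference is larger in one stratum than in the other. A comparison of responders with non-responders has another null hypothesis: that the feature is unrelated to outcome. A feature that raises improvement equally on ketamine and placebo violates that null with no moderation present. A real moderator can also be missed if patients with the feature do worse on placebo. At stake is the secondary question in the trial's own title, which at present has no pre-specified analysis that could answer it.

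**Working it through.** **The plan's own figure.** Eleven per group, for 60% against 10% response, follows from the unpooled two-sided formula: (1.960 + 0.842)² × (0.6×0.4 + 0.1×0.9) / 0.5² = 10.36, rounded up to 11. It concerns the ketamine-placebo main effect. No figure is given for moderation or predictors.

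**What each test targets.** Let a feature shift improvement by p on placebo and by p + δ on ketamine, so that δ is the moderation. On the scale of mean improvement:
- the ketamine-only comparison reflects p + δ;
- the pooled comparison reflects p + δ/2 with 1:1 allocation, or about p + 2δ/3 with 2:1;
- the interaction, (ketamine − placebo with the feature) − (ketamine − placebo without it), is δ alone.

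Only the last is free of p.

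**Illustration.** From the plan: a ketamine effect of 0.7 SD and two-sided alpha of 0.05. Assumed: normal improvement with SD 1; response means improvement above 0.7 SD; cells of 15/15/15/15 (N=60) or 15/15 ketamine with 8/7 placebo (N=45, the placebo split being assumed). Without a shift, response is 50% on ketamine and 24% on placebo. With p = 0.5 in the alcohol stratum it is 69% against 50% on ketamine and 42% against 24% on placebo. Rejection rates, from at least 40,000 simulated trials per row (chi-square without continuity correction):

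| Scenario | Responder test, ketamine only | Pooled, N=45 | Pooled, N=60 | Interaction |
|---|---|---|---|---|
| p = 0, δ = 0 | 5% | 4% | 4% | 5% |
| p = 0.5, δ = 0 | 18% | 20% | 30% | 5% |
| p = 0.8, δ = 0 | 39% | 47% | 64% | 5% |
| p = −0.5, δ = 1.0 | 18% | about 5% | 3% | 34% (N=45), 48% (N=60) |

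The algebra explains the last row. For ketamine only, p + δ = 0.5, the same as in row 2. For pooled N=60, p + δ/2 = 0, so the moderation cancels.

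**Check against the plan's response rates.** Take 70% and 50% on ketamine and 20% and 0% on placebo, with and without the feature. These average to the plan's 60% and 10%, and the risk difference is 50 points in both strata. With 15 per cell (8,000 trials), the pooled responder test rejects 32%, ketamine-only 20% and the interaction 6%. With N=45 the figures are 21%, 20% and 4%.

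**Power of the interaction.** SE = √(sum of 1/n over the four cells), in SD units; power = Φ(δ/SE − 1.96); the difference detectable with 80% power is 2.80 × SE.

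| Cells | SE | Power at δ = 0.7 | Detectable δ |
|---|---|---|---|
| 15/15/15/15 | 0.516 | 27% | 1.45 |
| 20/20/10/10 | 0.548 | 25% | 1.53 |
| 15/15/7.5/7.5 | 0.632 | 20% | 1.77 |

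The 95% CI half-width is 1.96 × SE: 1.01 SD in the first layout and 1.24 SD in the last. For 80% power at δ = 0.7 with equal cells, n per cell = 4 × (2.80/0.7)² ≈ 64.1, so 65, or 260 patients. The value 0.7 for δ is borrowed from the main effect.

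**The case against.** A reader might infer that the plan tests alcohol moderation with the responder comparison. It does not say so. Alcohol is a separate secondary analysis, and the sentence on Mann-Whitney and chi-square mentions neither alcohol nor moderation. For alcohol the defect is a missing method, not a stated wrong one, and the simulation shows only what would follow if the named test were used. A reader might also infer that prognostic factors will be reported as moderators. The documents do not say how these results will be labelled; the objective speaks of predictors, and the table may be meant as description. Nor is the responder comparison the only analysis named that involves baseline features, though none of the others contains a treatment-by-factor term.

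The size is also open to challenge. The shifts and the response threshold are assumed, and nothing is inflated when the feature is not prognostic. In that case the ketamine-only comparison can even detect true moderation more often: with response of 85% against 35% on ketamine and 10% in both placebo strata, it rejects 84%, against 72% for the interaction with 15 per cell. But that advantage depends on assuming there is no prognostic effect, and checking that assumption is what the placebo group is for.

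Finally, these are secondary aims with low power, and the layout needed for the interaction rests on Design alone. Both points stand. They limit what the fix can deliver but do not make a prognostic comparison an answer to a moderation question.

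**Conclusion.** The concern holds in a limited form. The plan has moderator and predictor aims and specifies no treatment-by-factor analysis for them. The named responder comparison tests prognosis whether or not arms are pooled, and the alcohol analysis has no method. This much is read directly from the text and needs no assumption.

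The size is conditional. An assumed 0.5 SD prognostic shift with no moderation gives 18% to 30% rejection, against about 5% for the interaction. Response patterns that average to the plan's 60% and 10% give 20% to 32% with 15 per cell. With no prognostic effect there is no inflation. The documents do not support saying that alcohol is assigned the wrong test or that prognostic factors will be called moderators. The plan should be amended; the primary ketamine-placebo comparison is not affected by this point.

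**What to change.** 1. Reconcile Description of Study Populations, Design, the allocation text after the list of measures, and inclusion criterion 4 on four matters: total N, allocation ratio, whether placebo patients are split by alcohol, and who has alcohol abuse. Without placebo patients in both strata the interaction cannot be estimated.
2. For the alcohol hypothesis, model 24-hour SSI change on arm, baseline SSI, alcohol stratum and arm × stratum. Report the interaction with its 95% CI as an estimate.
3. Use arm × feature in the same way for other candidate predictors. Description of Study Populations builds personal or family history of alcoholism into the alcohol subgroup, so a separate family-history term may be hard to tell apart from the alcohol term; say so in the plan.
4. Define responder. Show the responder table by arm and label it prognostic and descriptive.

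Cost: the reconciliation, some wording and one model term per feature. No new data are needed if the four-group layout in Design stands. The downside is low power: about 20% to 27% for a 0.7 SD difference between strata and 34% to 48% for 1.0 SD (both sizes assumed). The alcohol answer will be an estimate with a wide interval, and a non-significant interaction must not be read as absence of moderation.
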